6.3 Pharmacokinetics Variables

Plasma trough concentrations of TTP399 will be examined as variables of analysis.

7 Statistical Methodology

Descriptive statistics will be used to summarize the data. Continuous variables will be presented showing number of observations available, mean, median, minimum, maximum, and standard deviations (or standard errors, depending on the variable) by visit. Categorical variables will be presented showing frequencies and percentages by visit.

Efficacy analyses will also be done on the FAS and, potentially, also on the PPS. If the PPS differs from the FAS by more than 10%, the analyses will be replicated on the PPS. If the PPS and the FAS do not differ by more than 10%, analysis may not be done on the PPS. Final judgments will be made at the blind data review meeting in accordance with ICH E9.

All tests will be 2-sided and use $\alpha = 0.049$ for the final analysis to accommodate planned interim analyses for which $\alpha = 0.001$ is allocated, thereby preserving a study-wise over all $\alpha = 0.05$. This penalty is applied regardless of whether or not there is an actual modification to the study structure, design, or analysis plans.

Data displays will include the following comparisons:

- **Placebo**
- **800 mg TTP399.**

MedDRA version 21.0 or later will be used. SAS version 9.4 will be used.

7.1 Follow-up Visit Data

This study includes a safety evaluation 7 to 10 days after the final dose of study medication. Due to ethical considerations, it may be necessary to allow a patient to take a protocol-prohibited rescue medication, which would render objective interpretation of subsequent assessments impossible. Data obtained at the Follow-up assessment, therefore, cannot be included in efficacy or safety analysis as part of the statistical analysis planning for this study. Data captured at this visit will be reported and summarized in data tabulations and listings, but interpretation must proceed with due caution.

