7.3.2. Patient Withdrawal

Patients may withdraw from the study at any time at their own request, or they may be withdrawn at any time at the discretion of the Investigator or Sponsor for safety, behavioral, or administrative reasons.

If a patient does not return for a scheduled visit, every effort should be made to contact the patient. Every effort should be made to document patient outcome. The Investigator should inquire about the reason for withdrawal. The patient must return all unused study medication to the site and should return to the site for one or two visits, as described below.

Any AEs should be followed based on the following criteria:

Follow-up of any ongoing AE (including any clinically significant laboratory abnormality) should be conducted as follows:

- If the Investigator determines the AE is *not related* to the study product or study procedures, the AE will be followed until resolution, or 60 days from end of study participation.
- All AEs with a relationship other than *not related* will be followed until resolution, or until the patient is lost to follow-up.

At the discretion of the Investigator or designated licensed physician and Medical Monitor, the length of AE follow-up may be attenuated, with written rationale by the Investigator or designated licensed physician.

Upon termination, all patients who continue to consent will have a Follow-up Visit approximately 7-10 days after the last dose. Procedures leading up to the Follow-up Visit will depend on the patient's recent dosing and how long the patient has been on treatment. The following table summarizes what exit visits should be conducted upon termination assuming patient still consents:

Patient dosing/treatment status at termination:	Other applicable conditions:	Exit Visits to be conducted:
Patient has not received 4 weeks of treatment	None	Do not complete Early Termination visit. Conduct Follow-up Visit approximately 7-10 days after last dose.
Patient has not dosed within 10 days of initiating termination procedures	None	Do not complete Early Termination visit. Only conduct Follow-up Visit
Patient has dosed within 10 days of initiating termination procedures	Patient has reach 12 weeks of treatment (i.e., reached the Week 12 visit window of 12 weeks \pm 3 days). Patient will be considered to have completed treatment but not complete the study.	Do not complete Early Termination visit. Conduct Week 12 visit then a Follow-up Visit approximately 7-10 days later

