Double-blind Treatment Period (Day 1 though Week 12): It is noted that “week 12” and “day 84” are used interchangeably in this study, defining a month as 28 days and a week as 7 days. During the double-blind treatment period, daily doses of oral, double-blind study medication are administered. Efficacy, dosing compliance, and safety assessments are taken, including vital signs, adverse events, electrocardiography, and concomitant medications. Blood draws are taken for PK evaluations and for biomarkers.

Follow-up Visit (7-10 days after last dose): Approximately 7 to 10 days following the last dose of study medication, final safety assessments are taken, including vital signs, adverse events, ECG, and concomitant medications.

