7.7 Analysis of Safety Data

7.7.1 Adverse Events

Adverse events reported in this study will be coded using MedDRA®, Version 21.0 or later. Coding will be to the lowest level terms (LLT). The verbatim text, the preferred term, and the primary SOC will be listed in subject listings. Summaries that include frequencies and proportions of subjects reporting AEs will include the preferred terms and the SOCs.

Adverse event summaries will be done by study phase: (1) pre-dose,(2) placebo run-in, and (3) double-blind treatment phase, (4) period beginning with the first dose of double-blind medication, including follow-up phase. The final category is considered the primary summary of TEAEs to support comparisons of TTP399 with placebo.

Adverse events summaries will be constructed displaying AEs in decreasing order of total frequency according to the numbers of subjects reporting the AE (not the number of reports).

- Number (percent) of subjects reporting TEAE by Treatment and overall in accordance.

A listing will be constructed that includes the subject identification, the dose group, TEAEs, MedDRA terms, seriousness, severity, causality related to study medication, causality related to insulin, elapsed time to onset, duration, and outcome.

Adverse events of special interest (AESI) will include diabetic ketoacidosis and hypoglycemia.

For purposes of analysis and reporting, hypoglycemia events will be limited to those in the first two categories (severe hypoglycemia and documented symptomatic hypoglycemia) in accordance with FDA's regulatory guidance *Guidance for Industry Diabetes Mellitus: Developing Drugs and Therapeutic Biologics for Treatment and Prevention* (CDER, February 2008).

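### SAP 7.1 bars follow-up visit data from safety analysis, but SAP 7.7.1 builds the primary adverse-event comparison on a period that includes follow-up, and nothing restores follow-up laboratory, ECG or vital-sign data

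*SAP*

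**What the plan says.** SAP 7.1 (Follow-up Visit Data) starts from the possibility that "it may be necessary to allow a patient to take a protocol-prohibited rescue medication" and concludes that what is obtained at the follow-up visit "cannot be included in efficacy or safety analysis". It then adds a limited allowance: "Data captured at this visit will be reported and summarized in data tabulations and listings", to be interpreted with caution.

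SAP 7.7.1 (Adverse Events) lists four adverse-event summaries. The fourth is the "period beginning with the first dose of double-blind medication, including follow-up phase", and of it the SAP says: "The final category is considered the primary summary of TEAEs to support comparisons of TTP399 with placebo".

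SAP 1.8 confirms that at the follow-up visit "final safety assessments are taken, including vital signs, adverse events, ECG, and concomitant medications". Protocol 7.3.11 adds laboratory samples. Protocol Appendix 2 (Part 2) shows that these include chemistry, electrolytes, lipids, hematology, urine, lactate and beta-hydroxybutyrate (BOHB).

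For Part 2 patients who have received less than 4 weeks of treatment, the exit table in Protocol 7.3.2 (Patient Withdrawal) says: "Do not complete Early Termination visit. Conduct Follow-up Visit approximately 7-10 days after last dose". Patients who have not dosed within 10 days of starting termination procedures also have only a follow-up visit.

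**The concern.** One section excludes a class of data from safety analysis, and another uses the same class in the main safety comparison. An adverse event that starts after the last dose and is recorded at the follow-up visit is barred under 7.1 and counted under 7.7.1.

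For the other safety data there is no competing rule. SAP 7.7.3 to 7.7.5 (vital signs, laboratory, ECG) never say that follow-up values count, so 7.1 governs by default. A raised ALT, BOHB, lactate or QTc first seen at follow-up would then be left out of the proportions and criteria used to compare the arms. This matters most for patients whose only exit assessment is the follow-up visit, since they are the ones who stopped treatment early, possibly because of harm.

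The choice also affects counts. Two programmers working from the same SAP could reach different numbers, and the difference should not be settled after unblinding.

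**Working it through.** The point turns on text, so there is no plan figure to reproduce. The check has three steps.

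**1. Does each safety analysis have a rule that overrides 7.1?**

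- Adverse events (SAP 7.7.1): yes. The primary summary expressly includes follow-up. The SAP does not say which section prevails.
- Laboratory treatment-emergent abnormal values (TEAVs) and potentially clinically significant values (SAP 6.2.3, 7.7.4): no. The TEAV definition requires a normal value before dosing and an abnormal one after it, with no end date. These are described as proportions to be analyzed, so they fall within the bar.
- Liver-injury criteria (SAP 7.7.4), QTc categories (7.7.5) and vital signs (7.7.3): no. They are described as summaries and listings, which 7.1 might be read to allow, but they sit under the heading for analysis of safety data. On a literal reading the bar applies.
- Worst post-dose ECG value (7.7.5), and minimum, maximum and last-available summaries (8.10): neither section says whether a follow-up value counts.

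**2. Does the protocol settle it?** No. Protocol 10.7 contains no bar on follow-up data, includes all treated patients in the safety assessment, and promises descriptive statistics for each post-baseline assessment. But Protocol 10 also says that the SAP supersedes the protocol for analyses. SAP 1.11 lists two departures from the protocol, and this exclusion is not one of them.

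**3. Who depends on the follow-up visit?** Scheduled Part 2 laboratory draws after the first double-blind dose are at Week 2, Week 6, Week 12 or early termination (ET), and follow-up (Appendix 2). ECGs and vital signs follow the same visits (Protocol 8.4, 8.5). The table sets these against the exit table in Protocol 7.3.2.

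| Part 2 patient | ET visit | Scheduled post-dose data other than follow-up | Effect of 7.1 |
|---|---|---|---|
| Stops before the Week 2 visit | No | None | No scheduled post-dose laboratory, ECG or vital-sign value in safety analysis |
| Stops after Week 2, before 4 weeks | No | Week 2 | Only exit assessment lost |
| Has not dosed within 10 days | No | Scheduled visits already attended | Only exit assessment lost |
| At least 4 weeks, Week 6 not completed, dosed within 10 days | No row covers this case | Week 2 | Appears the same as the row above |
| Week 6 completed, dosed within 10 days, under 12 weeks | Yes, with laboratory samples | Weeks 2 and 6, ET | Exit assessment kept |

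The first row assumes that the patient does not attend the Week 2 visit after stopping. Such a patient is in the safety set (SAP 4), which needs only one dose.

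**The case against.** Much of the case on the other side stands.

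- **The data are not discarded.** A reader might infer that follow-up results disappear from the report. SAP 7.1 says that they are tabulated and listed. What is lost is their place in the analyses.
- **Serious signals have another route.** A reader might infer that a liver or QTc signal at follow-up would be missed. SAP 6.2 has untoward findings reported as adverse events whatever their source. Protocol 8.4, 8.5 and 8.7.2 record clinically significant post-dose abnormalities as adverse events. Protocol 9.8.4 treats potential drug-induced liver injury as a serious event, and Protocol 9.2 runs serious-event reporting through follow-up. The main exposure is abnormal values judged not clinically significant, which the TEAV and threshold analyses exist to count without relying on that judgment.
- **Not all early stoppers are affected.** A reader might infer that everyone who stops early loses exit laboratory data. Patients who completed Week 6 and dosed recently have an ET visit, and those who stop between Week 2 and 4 weeks keep a Week 2 draw.
- **The adverse-event conflict may resolve itself.** The more specific rule in 7.7.1 would probably be followed. The SAP does not say so, and this does nothing for laboratory, ECG and vital-sign data.
- **There is a reason for caution.** Rescue medication can change later values. But the reason is conditional, while the bar covers every patient, including those who took none. Flagging affected values meets the worry.

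**Conclusion.** The contradiction between SAP 7.1 and 7.7.1 is plain and needs correcting. For laboratory TEAV and potentially clinically significant proportions, 7.1 governs unopposed. For the liver-injury, ECG and vital-sign criteria this holds on a literal reading, and the text is at best unclear.

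The effect is concentrated in Part 2 patients who stop before 4 weeks or have not dosed within 10 days of termination, and is complete only for those who stop before Week 2. The number affected cannot be computed, because the documents give no dropout rate. The length of the follow-up window as a share of the study would not measure the loss either: laboratory tests, ECGs and vital signs are taken at single visits, and adverse events in that window are claimed by 7.7.1.

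The primary HbA1c comparison is not touched. This is a defect in safety rules that should be settled before unblinding.

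**What to change.** - Reword SAP 7.1 so that the exclusion applies to efficacy only. State that this includes the BOHB and lactate components of the primary responder definition (SAP 6.1.1). Their treatment-emergent wording has no end date, so follow-up values could otherwise change responder status.
- State that safety analyses (treatment-emergent adverse events, TEAVs, liver-injury, ECG and vital-sign criteria) use all data from the first double-blind dose through the follow-up visit, with values obtained after rescue medication flagged.
- Add an on-treatment-only display as support.
- Align SAP 7.7 and 8.10 with this, saying whether follow-up values enter the worst post-dose, minimum, maximum and last-available summaries.
- Record in SAP 1.11 any exclusion of follow-up safety data that is kept.

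The cost is SAP wording and one supportive display. No new data are needed.

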7.2 Patient Disposition

A tabulation of subject disposition will be presented, including the number screened, the number treated with single-blind placebo, the number randomized, the number dosed with double-blind study medication, the number who withdrew prior to completing the study, and reasons for withdrawal for those subjects who withdrew from the study prematurely.

Subjects who are randomized, but not dosed, will be included in disposition tables and listings. A summary table will include numbers of subjects available for analysis by population of analysis, including efficacy (by analysis subgroup) and safety (all treated subjects).

Subjects who withdraw from the study during the treatment period (who terminated treatment with study medication prematurely) will be displayed separately from subjects who withdraw from the study between the end of treatment and the follow-up visit. Randomized subjects who withdraw from the study prematurely will be listed with randomization identification, age, sex, race, ethnicity, treatment group, date of first dose of double-blind medication, date of last dose of double-blind medication, date of last visit, and reason for discontinuation.

7.3 Baseline Characteristics and Demographic Data

Demographic data will be summarized for the FAS, PPS, and SAF. Summaries of continuous variables will include number of subjects, mean, median, minimum, maximum, and standard deviation. Summaries of categorical variables will include numbers of subjects in each category, by treatment and overall. The variables to be summarized will include:

- Age, gender, and race
- Weight, height, BMI
- Baseline HbA1c
- Use of InPen or Pump
- Use of personal CGM

- Age at diagnosis
- Years since diagnosis.

7.4 Extent of Exposure and Treatment Compliance

Exposure to investigational product for the SAF will be summarized including the following variables:

- Treatment duration, calculated as the number of days from the date of first dose of double-blind mediation to date of last dose, inclusive.
- Total number of doses taken
- Total dose taken (mg of TTP399, with 0 mg for placebo)
- Compliance by visit for the active study period, calculated as the number of doses taken divided by the number of days on active study, multiplied by 100% and capped at 100% for any subject.
- Overall compliance, calculated as the number of doses taken divided by 83 (the protocol-specified number of days of dosing), multiplied by 100% and capped at 100% for any subject.

Descriptive statistics will be used for assessment of treatment exposure and treatment compliance within each treatment group and among treatment groups. Continuous variables will be presented showing number of observations available, mean, median, minimum, maximum, and standard deviations by visit and summarized for the study overall. Categorical variables will be presented showing frequencies and percentages by visit and for the study overall.

7.5 Methodology for Missing Data

In general, for safety, missing data will not be imputed. Missing baseline data will be imputed with the latest available pre-dose value. In the event that no pre-dose value is available, for safety data or for insulin data, the first available data will be used for the baseline comparisons.

In general, for analyses on measures, multiple imputation methodology will be used to accommodate missingness. For dichotomous variables, non-responder imputation is used.

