1.9 Sample Size and Power Considerations

The protocol includes sample size considerations for Part 2 of the study. The Part 1 of the study is considered to be a pilot study within the adaptive study protocol to obtain initial placebo-controlled, double-blind study data to support the progression of the investigation to Part 2.

The following statements pertain to sample size determination for Part 2:

“Assuming a standard deviation (SD) of 1%, 34 patients per group will provide 80% power to detect a difference between a group treated with TTP399 and the group treated with placebo of 0.7% in HbA1c using alpha = 0.049.

“Randomization of 68 patients (34 patients randomized to each arm) will provide adequate power for this study to meet its objectives related to HbA1c changes.

“Assuming 30% or fewer placebo-treated patients show improvement in HbA1c of 0.3% or better and assuming 60% or more patients treated with TTP399 will achieve improvement in HbA1c of 0.3% or better by Week 12, 49 patients per group will provide 80% power to detect a difference between TTP399 and placebo. Randomization of N=120 patients into the study to be included in the Part 2 analyses provides adequate power to achieve study objectives related to responder analysis.

“It is noted that the randomization stratification for part 2 will be reflected in the randomization identification with a stratum digit.

“It is noted that in this adaptive study, modification is permitted. (Section 10.2 of study protocol).

Rigorous calculations for the required sample size for the non-inferiority aspect of the study relative to the required sample size to achieve a conclusion of non-inferiority were not done during the development of the protocol. Using a non-inferiority margin of 0.3% (from the FDA guidance entitled Guidance for Industry Diabetes Mellitus: Developing Drugs and Therapeutics Biologics for Treatment and Prevention (CDER; February 2008), the sample size required for non-inferiority is bracketed by the sample size required for adequate power for superiority of HbA1c.

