- H_{15} : The mean change in time in hypoglycemia using 54 mg/dl as the threshold from baseline to Week 12 for the group treated with 800 mg TTP399 is not equal to that of the placebo group.

Conditional Fourth Statistical Evaluation:

- **Evaluation 7:**

Superiority on Quality of life Likert scale score is evaluated:

- H_{06} : The mean score for the single-item Likert scale for overall improvement in quality of life at Week 12 for the group treated with 800 mg TTP399 is equal to that of the placebo group.
- H_{16} : The mean score for the single-item Likert scale for overall improvement in quality of life at Week 12 for the group treated with 800 mg TTP399 is not equal to that of the placebo group.

3 Estimand Specification

This SAP is constructed to conform to regulatory guidance. In particular, this section is included as recommended by ICH E9 (R1) Addendum on estimands and sensitivity analysis in clinical trials to the guideline on statistical principles for clinical trials (30 August 2017).

In accordance with ICH E9 Addendum, the specification of the estimand is included in this SAP with the 4 attributes detailed in ICH E9 Addendum, Section A.3.1:

A. The Population, that is, the patients targeted by the scientific question:

For this study, the population consists of subjects with type 1 diabetes who meet eligibility requirements for the study, have qualified through the basal insulin-optimization period (if needed) and the placebo run-in period, receive double-blind medication, and have at least one valid post-baseline measure of HbA1c.

B. The variable (or endpoint) to be obtained for each patient, that is required to address the scientific question:

For this study, the primary endpoint is HbA1c with co-primary importance on treatment responsiveness (whether or not subjects are treatment responders).

C. The specification of how to account for intercurrent events to reflect the scientific question of interest:

For this study, intercurrent events such as blood transfusion or medical treatment with prednisone or major modification in insulin regimen/doses outside the once recommended in the protocol that would render subsequent values as not protocol-meaningful will be set to missing (moved to the SDTM SUPPLB domain to facilitate sensitivity analysis that includes the values) and primary statistical methodologies of multiple imputation will be used to predict what the values were likely to be had the intercurrent event not happened.

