cases will be judged for appropriateness for use in the primary estimand. Multiple imputation based on recursive regression will be used to predict unusable data for the primary analysis (supportive analysis will be done using all available data).

- Significant holidays including Thanksgiving Day and Christmas Day are excluded from analysis of CGM.

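### SAP 7.5 scores the co-primary responder as a failure when blinded review removes the Week 12 HbA1c, which does not match the SAP's own estimand for such values

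*SAP*

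**What the plan says.** **Status of the responder.** SAP Section 3, attribute B, gives treatment response co-primary importance next to HbA1c. SAP 6.1.1 lists the responder proportion as a primary variable. Its criteria are any fall in HbA1c, no treatment-emergent BOHB or lactic acid above the reference range, and no treatment-emergent severe hypoglycemia. Under SAP Section 2 the primary endpoint is met if non-inferiority holds (Evaluation 1) and, by Hochberg, either HbA1c superiority (Evaluation 2) or responder superiority (Evaluation 3) is shown.

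**Removed values.** Section 3, attribute C, and Section 8.4 set values affected by an intercurrent event to missing, after which "primary statistical methodologies of multiple imputation will be used to predict what the values were likely to be had the intercurrent event not happened". Section 8.2 has any HbA1c change above 1% queried and reviewed blind, and adds: "Multiple imputation based on recursive regression will be used to predict unusable data for the primary analysis".

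**Missing data.** Section 7.5 uses multiple imputation (MI) for measures. For the rest, "For dichotomous variables, non-responder imputation is used". It makes no exception for values that were observed and then removed.

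**Question asked.** SAP 5.1 and 5.2 describe patients without medications or transfusions that would distort HbA1c. SAP 5.5 names the placebo-subtracted responder proportion as a summary measure.

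**The concern.** Take a patient who has a transfusion and whose Week 12 HbA1c is set aside. Evaluations 1 and 2 predict the value the patient would have had without the transfusion. Evaluation 3 records treatment failure. The first is a hypothetical strategy. The second behaves like a composite strategy, in which the event itself counts as non-response. Attribute C states only the hypothetical strategy and does not exempt the responder named in attribute B.

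Non-responder imputation (NRI) can change the status only of patients who would otherwise have been responders, because someone whose HbA1c rose fails under either rule. A patient who improved by more than 1% and whose value is judged unusable under SAP 8.2 therefore becomes a failure, while a large worsener is unaffected. What is at stake is the result of a test that, once non-inferiority holds, can establish the primary endpoint on its own.

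**Working it through.** **Inputs.** Two-sided alpha is 0.049 (SAP Section 7). Part 2 has about 90 patients, 45 per arm (SAP 1.7). The planning rates in SAP 1.9 are 30% and 60%; they belong to the responder with a fall of at least 0.3%, not to the 6.1.1 composite, so they serve here only as an illustration. The removal rate is assumed.

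**Step 1: the plan's own figure.** SAP 1.9 states that "49 patients per group will provide 80% power to detect a difference between TTP399 and placebo". With z = 1.969 (alpha 0.049) and 0.842 (80% power), and a mean rate of 0.45:

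- n₀ = [1.969·√(2·0.45·0.55) + 0.842·√(0.30·0.70 + 0.60·0.40)]² / 0.30² = 42.2
- with continuity correction, n = (n₀/4)·[1 + √(1 + 4/(n₀·0.30))]² = 48.7, so 49

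The stated 49 reproduces. Exact Fisher power at 49 per group is 81.5%.

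**Step 2: power under NRI.** If removal is unrelated to response, the observed rate is the true rate × (1 − fraction removed). Power is by full enumeration of Fisher's exact test, 45 per arm, at 0.049. Under Hochberg that level applies to Evaluation 3 when Evaluation 2 is also at or below 0.049; otherwise the smaller p-value must reach 0.049/2 = 0.0245.

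| Removed (TTP399 / placebo) | Rates under NRI | Difference | Power |
|---|---|---|---|
| 0% / 0% | 60% vs 30% | 30 points | 75.3% |
| 10% / 10% | 54% vs 27% | 27 points | 66.6% |
| 15% / 15% | 51% vs 25.5% | 25.5 points | 62.4% |
| 10% / 0% | 54% vs 30% | 24 points | 54.3% |
| 0% / 10% | 60% vs 27% | 33 points | 84% |

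**Step 3: compared with imputation.** MI keeps the 30-point difference at some cost in precision, approximated here by a smaller arm.

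| Removed in both arms | NRI | MI (approximate) |
|---|---|---|
| 2% | 73.6% | 74.2% (44 per arm) |
| 5% | 70.9% | 73.7% (43 per arm) |
| 10% | 66.6% | 72.5% (40 per arm) |
| 15% | 62.4% | 68.1% (38 per arm) |

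**Step 4: single assumed datasets.** Both methods use a Wald test of the risk difference, with MI pooled by Rubin's rules, so that like is compared with like.

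| Observed TTP399 / placebo | Removed | NRI | MI |
|---|---|---|---|
| 25/41, 17/45 | 4 on TTP399 | 17.8 points, p = 0.086 | 23.2 points, p = 0.027 |
| 27/45, 16/41 | 4 on placebo | 24.4 points, p = 0.017 | 21.0 points, p = 0.046 |
| 26/43, 16/43 | 2 in each arm | 22.2 points, p = 0.030 | 23.3 points, p = 0.026 |

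In the first row the choice crosses 0.049 and in the second it crosses 0.0245, in opposite directions. In the third it changes nothing.

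**Step 5: who is affected.** A patient with no valid on-treatment HbA1c leaves the full analysis set (SAP Section 4), so neither rule applies. In the Part 2 laboratory table (protocol Appendix 2) the only other scheduled on-treatment HbA1c is at Week 6. A patient who fails the BOHB, lactate or severe-hypoglycemia criterion is a non-responder under both rules.

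**The case against.** A reader might infer that the SAP gives two explicit, opposing instructions, so that Evaluation 3 has two answers from the same data. The documents do not support that. Section 7.5 sorts methods by type of variable. Sections 5.4 and 8.4 send removed values to the planned missing-data methods, which for a dichotomous variable means 7.5. Protocol 10.6.3 likewise counts everyone not meeting the criterion as a non-responder, without imputation. No passage says responder status is multiply imputed, and attribute D of the Section 3 estimand is the mean difference in HbA1c change only. The direct reading gives one rule per endpoint.

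A reader might also infer that the rule works against TTP399, or that Section 8.2 automatically fails the best responders. Neither follows. Placebo-only removal widens the difference. Section 8.2 applies in both directions, a change above 1% only prompts a query, the judgment is blinded, and a supportive analysis with all available data is planned there; Section 8.4 plans another. Pairing MI for a continuous outcome with NRI for a binary one is common, and removals may be rare: steroids are restricted at entry and during the study, and a chronic transfusion requirement is an exclusion.

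All of this stands, and it limits the size of the point. It does not remove the mismatch. On the direct reading, Evaluation 3 is estimated by a rule at odds with attribute C and with the question in 5.1, 5.2 and 5.5. Protocol 10.6.3 does not settle it either: it does not address values removed by review, and protocol Section 10 lets the SAP supersede it.

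**Conclusion.** The point holds as a mismatch between estimand and estimator. As written, Evaluation 3 scores a transfusion, a steroid course or a removal at blinded review as treatment failure, although the SAP's estimand sets the event aside. The effect on the responder difference can be in either direction and depends on which arm has more removals. In the illustration, power runs from 54% to 84% around 75% at 10% removal. At 2% balanced removal the gap from imputation is 0.6 points (74.2% − 73.6%).

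These figures rest on assumed removal rates, removal unrelated to response, and planning rates set for a different responder definition. They show direction and scale and do not predict Evaluation 3. The change should be made before unblinding, because the test can decide the primary endpoint.

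**What to change.** In SAP 7.5 and 8.4, state that:

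- for an HbA1c removed under Section 3 attribute C, 8.2 or 8.4, the HbA1c component of the responder is derived in each of the imputed datasets used for Evaluation 2, and the logistic regression of SAP 7.6.1 is pooled over imputations;
- a patient who fails an observed BOHB, lactate or severe-hypoglycemia criterion is a non-responder regardless;
- NRI stays for every other missing Week 12 HbA1c, whether from dropout or from a missed or failed sample;
- scoring all missing and removed values as non-response is reported as a sensitivity analysis.

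Section 7.6 names Fisher's exact test for the responder, and it has no simple pooling rule. The text should therefore say that the 7.6.1 regression is the test for Evaluation 3.

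The cost is a few sentences and one derived variable in datasets that will exist anyway. The downsides are the pooling step and a less conservative handling of removed values, which the sensitivity analysis makes visible.
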